8.2.2.2. Reasons for Temporary Discontinuation of Study Drug

Study treatment may be temporarily stopped due to events that meet the criteria for treatment interruption described in Section 8.2.3 (and [Appendix 2](#)) or Section 8.3.

8.2.3. Immune-Mediated Adverse Events

8.2.3.1. Identification of Immune-mediated Adverse Events

Investigators must be extremely vigilant and be ready to intervene early in the management of imAEs, as the onset of symptoms of imAEs (eg, pneumonitis) may be subtle. An imAE can occur at any time during treatment or several months after the last dose of treatment. All AEs of unknown etiology associated with study drug exposure should be evaluated to determine possible immune etiology. If an imAE is suspected, efforts should be made to rule out neoplastic, infectious, metabolic, toxin or other etiologic causes prior to labeling an AE as an imAE.

Based on the emerging safety profile of cemiplimab and other antibodies targeting the PD-1/PD-L1 axis, working case definitions are provided in the Investigator's Brochure to help investigators distinguish imAEs from non-immune AEs commonly associated with PD-1 inhibition ([Naidoo, 2015](#)), ([Weber, 2015](#)). This is not exhaustive of all possible imAEs. Clinical presentations of less common imAEs, including neurologic, musculoskeletal, cardiac, renal, and ocular events ([Hofmann, 2016](#)), ([Zimmer, 2016](#)), should be reviewed in patients with concerning presentations.

The case definitions in the Investigator's Brochure have not been validated and are intended only as guidance for investigators to help distinguish imAEs from non-immune AEs. These definitions may evolve as clinical experience increases with cemiplimab and other antibodies targeting the PD-1/PD-L1 axis. Investigators' clinical judgment may include other factors when determining if an AE is immune-mediated.

8.2.3.2. Management of Immune-Mediated Adverse Events

Adverse events that meet the criteria for imAEs, as noted above in the Investigator's Brochure, should be reported as imAEs in the eCRF. If AEs corresponding to the common terms for imAEs are attributed as NOT related to cemiplimab by the investigator, additional information should be provided to substantiate an alternative attribution (eg, infectious diarrhea).

If not provided at the outset, this information may be requested by immediate edit checks or in subsequent queries. The sponsor may request additional information for any AE that is of a type known to be potentially immune-mediated (eg, rash, colitis, elevated transaminases, endocrine events), but is deemed not an imAE by the investigator.

Any grade 3 or greater imAE should be reported as an AESI (Section 10.2.3).

The following general principles apply to management of imAEs, unless otherwise specified in [Appendix 2](#):

Grade 1: Continue study treatment with close monitoring and provide symptomatic management

Grade 2: Consider withholding study treatment

Grade 3: Withhold study treatment

Grade 4: Discontinue study treatment

If cemiplimab is held for \leq grade 3 imAE, consider resuming when symptoms and/or laboratory values revert to baseline or \leq grade 1 after corticosteroid taper (typically, to ≤ 10 mg/day prednisone or equivalent).

Permanently discontinue study treatment for:

- Recurrent grade 3 imAEs
- Grade ≥ 3 or recurrent grade 2 Pneumonitis
- Grade ≥ 3 Hepatitis with AST/ALT $>5\times$ ULN or total bilirubin $>3\times$ ULN
- Grade ≥ 3 Nephritis with renal dysfunction
- Grade ≥ 3 Uveitis
- Grade ≥ 3 Neurologic toxicity
- Grade ≥ 3 Myocarditis or pericarditis
- Grade ≥ 3 Infusion related reaction
- Confirmed Stevens-Johnson syndrome (SJS), toxic epidermal necrolysis (TEN), or drug reaction with eosinophilia and systemic symptoms (DRESS)

- Grade ≥ 3 or recurrent grade 2 imAEs in patients previously treated with idelalisib
- Grade ≥ 3 infusion-related reaction
- Grade 2 or 3 imAEs persistent for ≥ 12 weeks after the last study treatment (excluding endocrinopathies)
- Requirement for ≥ 10 mg per day prednisone or equivalent lasting ≥ 12 weeks after the last study treatment

Further guidance regarding management of selected imAEs is provided in [Appendix 2](#). Additional information about the safety profile of cemiplimab is in the Investigators Brochure. Expert consensus guidelines that provide guidance managing less common imAEs are available and may be updated periodically ([Brahmer, 2018](#)) ([Haanen, 2017](#)) ([Puzanov, 2017](#)) ([Thompson, 2018](#)).

The management considerations provided here should not supersede clinical judgment in the setting of an individual patient. The investigator may choose to hold study treatment at his/her clinical judgment regarding the safety of an individual patient, even if hold criteria are not formally met per protocol.

Any patient currently receiving cemiplimab who was previously treated with a phosphatidylinositol 3-kinase (PI3K) inhibitor and who develops stomatitis or mucositis should temporarily suspend study treatment. If this or any other imAE occurs among these patients, the sponsor should be informed as soon as possible to discuss further management of the patient. An imAE of any grade in a patient previously treated with a PI3K inhibitor should be reported as an AESI.

8.2.4. General Guidance for Management of Adverse Events

This subsection provides general guidance of treatment-related AEs ([Table 1](#)) that are not specifically addressed in guidelines for management of imAEs (Section [8.2.3.2](#) or [Appendix 2](#)) or in management of acute infusion reactions (Section [8.3](#)). In the event of discrepancy between this section and a section that provides for detailed guidance (ie, Section [8.2.3.2](#), [Appendix 2](#) or Section [8.3](#)), the section that provides the more detailed guidance will supersede the general guidance in this section.

Table 1: General Guidelines for Management of Treatment-Related Adverse Events

Toxicity	Grade	Hold Treatment	Restarting Criteria
Hematological Toxicity (other than grade 3 thrombocytopenia greater than 7 days or associated with bleeding, or Grade 4 thrombocytopenia.)	1, 2, 3	No	N/A
	4	Yes	Toxicity resolves to grade ≤ 1 or baseline
Grade 3 thrombocytopenia greater than 7 days or associated with bleeding	3	Yes	Toxicity resolves to grade ≤ 1 or baseline

Toxicity	Grade	Hold Treatment	Restarting Criteria
Grade 4 thrombocytopenia	4	Yes	Discontinue permanently
Nonhematological Toxicity	1	No	N/A
Note: Exceptions to be treated as for Grade 1 toxicity:	2	Consider withholding for persistent symptoms	Toxicity resolves to grade ≤ 1

 Grade 2 alopecia Grade 2 fatigue Clinically insignificant lab abnormality not meeting criteria 	3	Yes	Toxicity resolves to grade ≤ 1
	4	Discontinue permanently	Discontinue permanently

N/A = not applicable

Treatment after an AE may resume at the discretion of the investigator if it is in accordance with the toxicity management guidelines in this protocol, if resumption of treatment is thought to be in the best interest of the patient and if either of the following conditions are met:

- After resolution of an AE to \leq grade 1 (or baseline)
- The AE is considered to be manageable through supportive/medical therapy (eg, grade 3 hypertension that can be controlled with the addition of a second anti-hypertensive agent).

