8.2.2.1. Reasons for Permanent Discontinuation of Study Drug

Study drug (cemiplimab and/or ISA101b) will be permanently stopped in the event of:

- Serious or severe allergic reactions considered related to study drug
- Grade 3 infusion related reaction
- Grade 3 uveitis
- Grade 3 or 4 neurologic toxicity
- Grade 3 or 4 myocarditis/pericarditis
- Any grade 4 non-hematologic toxicity except for clinically insignificant laboratory abnormalities
- Any non-hematologic toxicity that led to temporary withholding of study treatment which does not resolve to grade 1 or baseline within 12 weeks of last study drug infusion except for immune-mediated endocrinopathies controlled with hormonal therapy
- Grade 4 hematologic toxicity that does not resolve to less than grade 4 within 2 weeks of last infusion or to grade 2 (neutropenia) or grade 1 or baseline (others) within 12 weeks of last study drug infusion.
- Physician/patient decision
- Treatment delay of ≥ 84 consecutive days from last dose of study drug

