9. STUDY SCHEDULE OF EVENTS AND PROCEDURES

9.1. Schedule of Events

Study assessments and procedures are presented by study period and visit in [Table 2](#).

The allowable window for all visit days and assessments is ± 3 business days (excluding weekends and holidays), unless otherwise stated. All other "days" in the protocol refer to calendar days. For tumor assessments (CT or MRI), the window is ± 7 days from planned scan dates, unless otherwise stated.

Missed doses of cemiplimab or visits will not be made up. In the case of missed doses of cemiplimab, tumor assessments should still follow original schedule. If a patient is unable to undergo scans within the window due to logistical or medical reasons, tumor assessment will be obtained at the next available date.

Missed doses of ISA101b are detailed in Section [8.3.1.3.1](#).

In light of the public health emergency related to COVID-19, the continuity of clinical study conduct and oversight may require implementation of temporary or alternative mechanisms. Examples of such mechanisms may include, but are not limited to, any of the following: phone contact, virtual visits, telemedicine visits, online meetings, non-invasive remote monitoring devices, use of local clinic or laboratory locations, and home visits by skilled staff. Additionally, no waivers to deviate from protocol enrollment criteria due to COVID-19 will be granted. All temporary mechanisms utilized, and deviations from planned study procedures are to be documented as being related to COVID-19 and will remain in effect only for the duration of the public health emergency.

Table 2: Schedule of Events

Study Procedure	Screening Visit ¹	Cycle 1 ^{2,3}				Cycle 2 to 4 ^{2,3}			Cycles 5+ ^{2,3}				EOT Visit ^{4,5}	Safety Follow-up ^{4,5}	Tumor Assessment ⁵	Survival Follow-up ^{4,5}
	Day -28 to Day -1	Day 1	Day 8 ±3	Day 29 ±3	Day 50 ±3	Day 1 ±3	Day 22 ±3	Day 43 ±3	Day 1 ±3	Day 22 ±3	Day 43 ±3	Day 64 ±3	30 days after last dose ±7 days	90 days after last dose ±10 days	Every 4 months (±10 days)	Every 4 months (±10 days)
Inclusion/exclusion	X															
Informed consent ⁶	X															
Genomics substudy informed consent (optional)	X															
PBMC consent (optional)	X															
Future biomedical research consent (optional)	X															
Medical history and demographics	X															
Electrocardiogram ⁷	X												X	X		
Performance status	X												X	X		
Tumor tissue sample	X ⁶															
Treatment:																

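### Protocol 8.2.4 gives two different rules for restarting cemiplimab after a treatment-related grade 3 non-hematologic AE, and the permanent-stop rule in 8.2.2.1 recognises only part of the wider one

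*Protocol*

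**What the plan says.** Section 8.2.4 of the protocol covers treatment-related AEs that are not dealt with in 8.2.3.2, Appendix 2 or 8.3. If it differs from one of those sections, the more detailed section prevails.

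- **Table 1, non-hematologic toxicity, grade 3:** hold treatment; restart when "Toxicity resolves to grade ≤ 1". The grade 2 row has the same restart criterion.
- **Table 1, hematologic rows that call for a hold with possible restart:** "Toxicity resolves to grade ≤ 1 or baseline".
- **Paragraph below Table 1:** the investigator may resume treatment if this is in the patient's best interest, "if it is in accordance with the toxicity management guidelines in this protocol", and "if either of the following conditions are met". The first condition is resolution to grade 1 or lower, or to baseline. The second is "The AE is considered to be manageable through supportive/medical therapy (eg, grade 3 hypertension that can be controlled" by adding a second antihypertensive).
- **Section 8.2.2.1, permanent discontinuation:** "Any non-hematologic toxicity that led to temporary withholding of study treatment which does not resolve to grade 1 or baseline within 12 weeks" of the last infusion. Immune-mediated endocrinopathies controlled with hormones are excepted. A separate item stops drug once the delay from the last dose reaches 84 consecutive days.
- **Section 9.1:** "Missed doses of cemiplimab or visits will not be made up".

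**The concern.** The protocol's own example of a manageable AE, grade 3 hypertension, is a grade 3 non-hematologic toxicity. When it is treatment-related, Table 1 requires resolution to grade 1 or lower, while the text beneath it asks only that the AE be manageable. Two sites could treat the same patient differently and each cite 8.2.4.

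What is at stake is re-exposure to cemiplimab with a persisting grade 3 AE on one side, and loss of treatment for an AE that the protocol itself describes as manageable on the other. The choice also feeds into reported results: reasons for treatment discontinuation (protocol 11.4.1, SAP 5.4), and exposure and relative dose intensity (protocol 11.4.5.3, SAP 5.6.2). It decides too whether a given restart counts as a protocol deviation (SAP 5.5).

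**Working it through.** The plan states no figure on this point, so there is none to reproduce. The check is a comparison of texts followed by a count of doses.

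**1. Two test patients, each with a treatment-related grade 3 non-hematologic AE outside 8.2.3.2, Appendix 2 and 8.3**

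| Situation after the hold | Table 1 | Paragraph below Table 1 | 8.2.2.1 |
|---|---|---|---|
| A. Hypertension still grade 3, controlled with a second drug, above baseline | No restart | May resume (second condition) | Not resolved to grade 1 or baseline: permanent stop at 12 weeks |
| B. AE back to a baseline of grade 2 | No restart | May resume (first condition, baseline) | Resolution item satisfied; the 84-day delay item still applies if the hold continues |

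Table 1 and the paragraph disagree on both patients. For B, 8.2.2.1 uses the same resolution threshold as the paragraph's first condition. For A, it has no counterpart to the second condition. The one exception it makes for a controlled toxicity is for immune-mediated endocrinopathies.

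**2. Does anything rank the table against the text?**

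- The precedence sentence ranks 8.2.3.2, Appendix 2 and 8.3 above 8.2.4. It does not rank two parts of 8.2.4, and none of those sections addresses hypertension as a treatment-related AE.
- The requirement that resumption be "if it is in accordance with the toxicity management guidelines in this protocol" could be read as making Table 1 control. The second condition would then have no effect for its own example when that AE is treatment-related, and the baseline wording would have none for treatment-related non-hematologic AEs.
- Table 1 lists exceptions to be handled as grade 1 (grade 2 alopecia, grade 2 fatigue, clinically insignificant laboratory abnormalities). Controlled grade 3 hypertension is not among them.

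**3. Doses planned before the cycle 4 day 43 scan**

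Inputs from protocol 6.1: cemiplimab on days 8 and 29 of cycle 1 and on days 1 and 22 of cycles 2 to 4; cycle 1 lasts 7 weeks and cycles 2 to 4 last 6 weeks each.

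- Number of doses: 2 + 3 × 2 = 8.
- First days of cycles 2, 3 and 4: study days 50, 50 + 42 = 92 and 92 + 42 = 134.
- Dosing days: 8, 29, 50, 71, 92, 113, 134 and 155, each 21 days apart.
- Cycle 4 day 43: 134 + 42 = study day 176, which is 175 / 7 = 25 weeks after day 1. Section 9.1.2 calls this the primary endpoint visit.

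**4. Doses missed during a hold that is never lifted**

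- Stop limit: 12 × 7 = 84 days from the last dose, so the 12-week and 84-day items coincide.
- Doses due after the last one: days 21, 42, 63 and 84. The first three are missed during the hold; the fourth falls on the day the stop applies.
- Share of the 8 planned doses: 3 / 8 = 37.5%. All three fall before the cycle 4 day 43 scan if the last dose given was one of the first five (5 + 3 = 8).
- Doses due from day 84 on are lost through the permanent stop itself.

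**The case against.** The strongest defence is that the paragraph is cumulative: discretion, best interest, agreement with the toxicity guidelines, and only then one of the two conditions. On that reading Table 1 is one of the guidelines, and the two conditions add to it without overriding it. The paragraph also speaks of an AE in general, whereas Table 1 concerns treatment-related AEs, so the manageable route could still serve AEs not attributed to treatment. It stands that there is no conflict for unrelated AEs. The rest does not remove the problem: 8.2.4 is expressly about treatment-related AEs, and nothing tells a site that the second condition is closed to them.

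The scope is also narrow, and that stands. ISA101b restart is governed by 8.3.1.3.1, which requires resolution to grade 1 or lower or baseline (grade 2 fatigue excepted) and prevails as part of 8.3. Immune-mediated AEs follow 8.2.3.2 and Appendix 2. Infusion reactions of grade 3 or higher end treatment under 8.3.1. What remains is cemiplimab restart after other treatment-related grade 3 non-hematologic AEs.

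Finally, it can be said that no endpoint or analysis set changes. That is correct: ORR is analysed in all treated patients (protocol 11.3.1 and 11.4.3.1).

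**Conclusion.** The inconsistency is real and lies in the current text of 8.2.4. For treatment-related grade 3 non-hematologic AEs outside the more detailed sections, the table and the paragraph beneath it give different conditions for restarting cemiplimab, and 8.2.2.1 matches only part of the paragraph. For a patient with a controlled but persisting grade 3 AE, the outcomes range from resuming at the investigator's discretion to 3 missed doses during the hold followed by a permanent stop.

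The dose count assumes nominal visit days, no resolution during the hold, and an 84-day clock running from the last cemiplimab dose. The number of such patients cannot be derived from the documents.

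A reader might infer more than the documents support:

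- *Section 8.2.2.1 sets a third threshold.* It does not. Its resolution level is that of the paragraph's first condition, and it is a stop rule, not a restart rule.
- *Four doses, half of the planned eight, are missed.* Dividing 12 weeks by 3 counts intervals. The dose at the end of the fourth interval coincides with the stop.
- *Table 1 itself takes the patient off drug.* For grade 3 it only prolongs the hold; the permanent stop comes from 8.2.2.1.
- *The patient may resume at once.* Resumption still needs investigator discretion and the patient's best interest.
- *ORR is biased.* Nothing in the documents allows that to be shown.

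This is a wording inconsistency that should be corrected. It is not a flaw in the estimation of the primary endpoint.

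**What to change.** The sponsor should reconcile three texts: the non-hematologic rows of Table 1, the resumption paragraph in 8.2.4, and the unresolved-toxicity item in 8.2.2.1. The revised wording should answer two questions:

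1. Does return to baseline permit restart after a non-hematologic toxicity, as it does in the hematologic rows?
2. Does the manageable route apply to treatment-related AEs? If so, Table 1 and 8.2.2.1 need to say so; if not, the paragraph needs to say so and its example needs to be consistent with that.

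Which rule is right is a clinical decision for the sponsor, and none is proposed here.

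The cost is the wording of two table rows and a few sentences, issued as a clarification letter or in the next amendment (with the ethics review that protocol section 14 requires), plus a notice to sites. Sample size, endpoints, analysis sets and SAP methods are unchanged.

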8.3. Management of Acute Reactions

8.3.1. Acute Intravenous Infusion Reactions

Infusion-related reactions (IRRs) are known to occur with infusions of therapeutic proteins and have been observed in cemiplimab studies. To assist investigators in identifying IRRs, the following case definition is provided:

- Typical symptoms may include fever, chills, rigors, skin flushing, dyspnea, back pain, abdominal pain, and nausea
- Infusion reactions usually occur either during the infusion or within 24 hours after the infusion is completed
- Vital signs may be notable for hypotension and/or tachycardia
- Signs and symptoms generally resolve completely within 24 hours of onset

The investigator's clinical judgment may include other factors when evaluating a possible IRR.

See the Investigator's Brochure for further information about IRRs with cemiplimab. Such reactions may also be referred to as systemic hypersensitivity reactions.

Emergency equipment and medication for the treatment of infusion reactions must be available for immediate use. All infusion reactions must be reported as AEs (as defined in Section 10.2.4) and graded using the grading scales as instructed in Section 10.2.5.

In the event of an infusion reaction of \geq grade 3 severity during or directly following infusion of cemiplimab, dosing should be stopped, and the patient must be permanently discontinued from study treatment.

Case report forms must capture start and stop time of the event, signs and symptoms, and management interventions (medications, interruption of infusion, rate reduction).

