4.2. Secondary Endpoints

The secondary endpoints are:

- Incidence and severity of TEAEs/adverse events of special interest (AESIs)/serious adverse events (SAEs) and \geq grade 3 laboratory abnormalities during the treatment period and up to 90 days after the last dose of study treatment
- DOR
- PFS
- OS

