6. STUDY DESIGN

6.1. Study Description and Duration

This will be a single-arm, phase 2, global study of treatment with cemiplimab + ISA101b in HPV16-positive cervical cancer patients with disease progression on first line chemotherapy in the recurrent or metastatic setting. Study treatment and duration include cemiplimab every 3 weeks (with 3 doses of ISA101b on days 1, 29, and 50) until progression or any reason for early discontinuation as outlined in Section 7.3 and Section 8.2.2.

Patients will undergo screening evaluations to determine eligibility within 28 days prior to first treatment. All patients will receive the following regimen:

- ISA101b 100 µg/peptide by SC injection on day 1, day 29, and day 50 (total of 3 doses).
- Cemiplimab 350 mg given by IV infusion over 30 minutes Q3W on days 8 and 29 in cycle 1, on days 1 and 22 in cycles 2 through 4, and on days 1, 22, and 43 in all subsequent cycles or until disease progression or discontinuation of study drug for any other reason.

[figure not shown]
Note: On days 29 and 50, cemiplimab will be administered first, and ISA101b will be administered approximately 1 hour after the end of the cemiplimab infusion. Patients must be observed for 4 hours after each ISA101b administration.

The timing of doses is summarized in Figure 2. Cycle 1 will be 7 weeks long, cycles 2 through 4 will be 6 weeks long, and all subsequent cycles will be 9 weeks long.

Patients will be assessed for response at cycle 1 day 50 (week 7), then once per cycle (every 6 weeks for 3 cycles, then every 9 weeks in all subsequent cycles or until disease progression or discontinuation of study drug for any other reason; Section 8.8, Section 8.2.2, and Section 7.3, respectively). Patients with confirmed CR after a minimum of 48 weeks of treatment may elect to discontinue treatment and continue with all relevant study assessments (eg, efficacy assessments).

There will be a 90-day safety follow-up after the last dose of cemiplimab. Patients who discontinue study drug for reasons other than progression will be followed approximately every 4 months by scans until disease progression or until the patient commences another anticancer systemic therapy, whichever comes first. After progression, survival follow-up should occur approximately every 4 months.

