The total duration of study from start of screening to final analysis of OS is expected to be approximately 36 months (approximately 12 months of accrual, approximately 12 months of treatment, and approximately 12 months of follow up).

Figure 2: Study Flow Diagram

¹ Withdrawal due to reasons as listed in Section 7.3 and Section 8.2.2.

End of treatment is defined as the end of study drug. Patients may discontinue study drug for progression of disease or for any reason listed in Section 7.3 and Section 8.2.2. Thirty days after the last dose of study drug, patients will have EOT visit. Ninety days after the last dose of study drug, patients will have the safety follow-up visit (Table 2).

A patient who progresses on treatment will have EOT visit and safety follow-up visit. End of study (EOS) disposition will be on or after the safety follow-up visit. They will then enter survival follow-up.

A patient who discontinues treatment for reasons other than progression, as listed in Section 7.3 and Section 8.2.2, will have EOT and safety follow-up visit. They will then have tumor assessments until progression or the start of another anticancer therapy. At progression or start of another anticancer therapy, patients will have EOS disposition and then enter survival follow-up.

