8.2. Dose Modification and Study Treatment Discontinuation Rules

8.2.1. Dose Modification

Dose modification of cemiplimab for an individual patient is not allowed.

If cemiplimab is delayed, interrupted, or discontinued due to toxicity clearly related to cemiplimab as described in the cemiplimab Investigator's Brochure, and this toxicity is not considered related to ISA101b, the remaining doses of ISA101b may be administered. It is recommended to discuss such cases with the Medical Monitor.

If ISA101b is delayed, interrupted, or discontinued due to toxicity clearly related to ISA101b as described in the ISA101b Investigator's Brochure, and this toxicity is not considered related to cemiplimab, the remaining doses of cemiplimab may be administered. It is recommended to discuss such cases with the Medical Monitor.

There will be no dose reduction for ISA101b in this study.

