10. SAFETY EVALUATION AND REPORTING

10.1. Recording and Reporting Adverse Events

10.1.1. Adverse Events

The investigator (or designee) will seek information on AEs at each patient contact, and record all AEs that occur from the time the informed consent is signed until 90 days after the last study treatment, or until the patient commences another anticancer systemic therapy, whichever comes first. After informed consent has been obtained but prior to initiation of study drug, only the following AEs should be reported:

- SAEs
- Non-SAEs caused by a protocol-mandated intervention (eg, non-SAEs related to invasive procedures such as biopsies)

Other AEs that occur prior to the first treatment should be reported on the medical history CRF.

All AEs after initiation of study treatment and until 90 days after the last study treatment, regardless of relationship to study treatment, will be reported on the AE CRF. Additionally, any SAE or other AE of concern that the investigator believes may be related to study treatment and that occurs later than 90 days after last study treatment, or after the patient has commenced another anticancer systemic therapy (whichever comes first) should be reported.

Study treatment includes cemiplimab and ISA101b.

Information on follow-up for AEs is provided in Section 10.1.2. Laboratory, vital signs, or ECG abnormalities are to be recorded as AEs as outlined in Section 10.1.5.

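### The protocol both permits and forbids further ISA101b after a permanent stop for cemiplimab toxicity, and gives two dates for the 90-day safety visit when ISA101b outlasts cemiplimab

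*Protocol*

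**What the plan says.** **Which drug stops.** Protocol 8.2.1 opens "If cemiplimab is delayed, interrupted, or discontinued due to toxicity clearly related to cemiplimab" and, provided the toxicity is not considered related to ISA101b, concludes "the remaining doses of ISA101b may be administered". It recommends discussing such cases with the Medical Monitor.

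Protocol 8.3.1 deals with grade 3 or higher reactions to a cemiplimab infusion: "dosing should be stopped, and the patient must be permanently discontinued from study treatment". Protocol 8.2.3.2 heads its list of immune-mediated and other events "Permanently discontinue study treatment for". Protocol 10.1.1 states "Study treatment includes cemiplimab and ISA101b". Protocol 8.2.2.1, whose list includes the grade 3 infusion reaction, says that one drug or both will be stopped, but does not say which drug for which event.

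**When follow-up ends.** Protocol 6.1 first says "There will be a 90-day safety follow-up after the last dose of cemiplimab". The synopsis and SAP 2.3 say the same. Further on, 6.1 says "Ninety days after the last dose of study drug, patients will have the safety follow-up visit". The column header in Table 2 refers to 90 days after the last dose, with a 10-day window either side, and names no drug. The safety endpoint in 4.2 runs "up to 90 days after the last dose of study treatment". The adverse event reporting period (10.1.1) and the on-treatment period (Protocol 11.4.5.1, SAP 4.5) likewise run from the last study treatment or study drug.

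**The concern.** A site with a patient who has a severe reaction to cemiplimab early in cycle 1 must decide whether to give up to two more vaccine doses. Read literally, the current text supports both answers, so patients with the same event could be treated differently depending on the section consulted. The choice matters for safety. Section 8.3.1 notes that infusion reactions may also be called systemic hypersensitivity reactions, and 1.3.3 describes systemic allergic reactions as potentially the most serious reactions to the vaccine.

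The second issue arises only if 8.2.1 is followed. ISA101b can then be the last drug given, and a safety visit dated from cemiplimab falls before the safety-endpoint window closes. Table 2 places the last scheduled hematology and chemistry at that visit, and laboratory abnormalities of grade 3 or higher are part of the secondary safety endpoint.

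**Working it through.** There is no plan figure to reproduce. The check compares the clauses and then does date arithmetic on the protocol's own dose days.

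**Step 1: one event under each clause.** Take a grade 3 infusion reaction on day 8, the first cemiplimab dose, clearly related to cemiplimab.

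- 8.2.1: the day 29 and day 50 ISA101b doses may be given.
- 8.3.1 with 10.1.1: study treatment, meaning both drugs, stops permanently.
- 8.2.2.1: one drug or both; unspecified for this event.
- 8.2.4 has a precedence sentence, but it only places 8.2.4 below 8.2.3.2, Appendix 2 and 8.3. It does not rank 8.2.1 against 8.3.1 or 8.2.3.2.

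**Step 2: which 8.2.3.2 events can clash.** An event clashes only if a vaccine dose is still due. Two listed items require 12 weeks (84 days) after the last study treatment: persistent grade 2 or 3 events, and a continuing steroid requirement. The earliest first cemiplimab dose is day 8 − 3 = 5, so these items cannot be met before day 5 + 84 = 89. The last possible ISA101b dose under 8.3.1.3.1 is day 66 + 3 = 69. These two items cannot clash. Items without a 12-week condition can arise while doses remain.

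**Step 3: the safety visit date.** Inputs: ISA101b on days 1, 29 and 50 (6.1), with a make-up third dose on day 66 (8.3.1.3.1); cemiplimab on days 8 and 29 in cycle 1, then at the start of cycle 2, taken as day 50. Visit date = anchor day + 90.

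| Last cemiplimab (day) | Last ISA101b (day) | Visit from last cemiplimab | Visit from last study drug | Difference (days) |
|---|---|---|---|---|
| 8 | 50 | 8 + 90 = 98 | 50 + 90 = 140 | 42 |
| 8 | 66 | 8 + 90 = 98 | 66 + 90 = 156 | 58 |
| 29 | 50 | 29 + 90 = 119 | 50 + 90 = 140 | 21 |
| 29 | 66 | 29 + 90 = 119 | 66 + 90 = 156 | 37 |
| 50 | 66 | 50 + 90 = 140 | 66 + 90 = 156 | 16 |
| 50 | 50 | 140 | 140 | 0 |

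If cemiplimab continues after ISA101b stops, the last study drug is cemiplimab and the difference is 0. The dates separate only when ISA101b is given after the last cemiplimab dose.

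**Step 4: does the visit window absorb the difference?** In the first row, 98 ± 10 gives days 88 to 108 and 140 ± 10 gives days 130 to 150. They do not overlap. Even a visit on day 108 is 140 − 108 = 32 days before the endpoint window closes. Measured from the last vaccine, the day 98 visit comes 98 − 50 = 48 days after a day 50 dose, or 98 − 66 = 32 days after a day 66 dose.

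**The case against.** The strongest reply is that 8.3.1 and 8.2.3.2 never say that both drugs stop. That meaning comes from an adverse event reporting section, and Section 8 uses the term loosely. Section 8.3.1.1 applies it to infusions, although only cemiplimab is infused, and 8.2.3.2 moves from withholding study treatment to cemiplimab being held. On this view the stop rules could mean cemiplimab alone. Alternatively, the permission in 8.2.1, which is conditional and comes with advice to consult the Medical Monitor, could be read as limited by the mandatory wording in 8.3.1. Both readings are reasonable, but they lead to opposite actions and the text does not choose between them. Elsewhere, as in 8.3.1.3.1, the protocol names ISA101b when it means that drug alone.

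The second reply is that data capture does not depend on the visit. This largely stands. Adverse events must be recorded until 90 days after the last study treatment, every analysis window uses that anchor, 8.2.2 asks patients to return for remaining visits, and the later text of 6.1 gives the later date. What remains is that a site following the cemiplimab-anchored sentence would hold the last scheduled safety visit and laboratory tests early.

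A reader might also infer that the 12-week and 84-day limits in 8.2.2.1 contradict each other, because one runs from the last infusion and the other from the last dose of study drug. The documents do not support that. The first limits unresolved toxicity and the second limits treatment delay; they are separate triggers, and whichever is met first applies. At most, the drug meant in the delay limit could be stated.

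**Conclusion.** The point holds as a contradiction in current text with a limited reach. For events that can occur while vaccine doses remain, 8.2.1 permits what 8.3.1 and 8.2.3.2, read with 10.1.1, forbid. When ISA101b is given after the last cemiplimab dose, the 90-day safety visit has two dates: 42 days apart with dosing to day 50 and 58 days apart with a day 66 make-up dose, if cemiplimab was last given on day 8. Later cemiplimab stops give smaller differences.

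Three stronger readings are not supported. Not every item in 8.2.3.2 clashes, because the two 12-week items come too late. Safety-endpoint data are not lost by design, since adverse event recording continues; the exposure is in the timing of the last scheduled visit and laboratory tests. Table 2 does not settle the anchor, because it names no drug.

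The dates assume nominal dose days and no new anticancer therapy before the window closes, since that would end adverse event collection earlier. The number of patients affected is likely small, but the documents give no rate. Response rate is not directly changed. No view is taken here on which clinical rule is right.

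**What to change.** The sponsor should reconcile Protocol 8.2.1, 8.2.2.1, 8.2.3.2 and 8.3.1 by stating, for each permanent-stop event, whether cemiplimab, ISA101b or both are stopped. Appendix 2 uses the same term and should be aligned. The choice of rule is the sponsor's.

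The sponsor should also reconcile the synopsis, the first follow-up sentence in 6.1 and SAP 2.3 with the later text in 6.1 and with Table 2, so that a single anchor is used for the 90-day visit and is consistent with the safety-endpoint window. Table 2 should name the drug to which its last dose refers. Optionally, 8.2.2.1 could state which drug the 84-day delay limit concerns.

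The cost is wording in the protocol, through the usual amendment approval, and one sentence in the SAP. Depending on the anchor chosen, the safety visit may move for a few patients. Sample size and the efficacy analysis are unaffected.
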